6.5 Overdose

The IMP in this study is administered at the study site under oversight by the site staff. Hence the risk for an overdose is considered low. There is no experience of overdose and no antidote to AZD1419. In cases of known or suspected overdose, symptomatic treatment and monitoring of vital functions and e.g. haematology parameters should be performed according to routine clinical practice based on the judgment of the investigator. In addition, should an overdose occur the following procedures should be followed:

- An overdose with associated AEs is recorded as the AE diagnosis/symptoms on the relevant AE modules in the CRF and on the Overdose CRF module.
- An overdose without associated symptoms is only reported on the Overdose CRF module.

If an overdose on an AstraZeneca study drug occurs in the course of the study, then the Investigator or other site personnel inform appropriate AstraZeneca representatives immediately, or **no later than 24 hours** of when he or she becomes aware of it.

The designated AstraZeneca representative works with the Investigator to ensure that all relevant information is provided to the AstraZeneca Patient Safety data entry site.

For overdoses associated with a SAE, the standard reporting timelines apply, see Section 6.4. For other overdoses, reporting must occur within 30 days.

6.6 Pregnancy

All pregnancies and outcomes of pregnancy should be reported to AstraZeneca.

6.6.1 Maternal exposure

If a patient becomes pregnant during the course of the study investigational product should be discontinued immediately.

Pregnancy itself is not regarded as an adverse event unless there is a suspicion that the investigational product under study may have interfered with the effectiveness of a contraceptive medication. Congenital abnormalities/birth defects and spontaneous miscarriages should be reported and handled as SAEs. Elective abortions without complications should not be handled as AEs. The outcome of all pregnancies (spontaneous miscarriage, elective termination, ectopic pregnancy, normal birth or congenital abnormality) should be followed up and documented even if the patient was discontinued from the study.

If any pregnancy occurs in the course of the study, then the Investigator or other site personnel informs the appropriate AstraZeneca representatives within 1 day i.e., immediately but **no later than 24 hours** of when he or she becomes aware of it.

The designated AstraZeneca representative works with the Investigator to ensure that all relevant information is provided to the AstraZeneca Patient Safety data entry site within 1 or 5 calendar days for SAEs (see Section 6.4) and within 30 days for all other pregnancies.

The same timelines apply when outcome information is available.

The PREGREP module in the CRF is used to report the pregnancy and the PREGOUT is used to report the outcome of the pregnancy.

6.6.2 Paternal exposure

Male patients should refrain from fathering a child or donating sperm during the treatment and until 1 month following the last dose of IMP.

Pregnancy of the patient's partners is not considered to be an adverse event. However, the outcome of all pregnancies (spontaneous miscarriage, elective termination, ectopic pregnancy, normal birth or congenital abnormality) should if possible be followed up and documented. To capture information about a pregnancy from the partner of a male patient, the male patient's partner consent must be obtained to collect information related to the pregnancy and outcome;

the male patient should not be asked to provide this information. A consent form specific to this situation must be used.

6.7 Management of IMP related toxicities/Dose Reductions

For information on the Dose adaptation scheme, please see Section 4.2.2.

6.8 Study governance and oversight

The safety of the patients in this clinical trial is closely monitored on an on-going basis by AstraZeneca representatives including the study physician. Issues identified will be addressed; for instance this could involve amendments to the study protocol and letters to Investigators.

In addition there is also a Data Safety Monitoring Board (DSMB), see below.

6.8.1 Data Safety Monitoring Board

An internal AstraZeneca Data Safety Monitoring Board (DSMB) that is independent of the study team will be appointed for the study. The DSMB will consist of at minimum a physician as clinical representative and a representative from Patient Safety. The DSMB will be responsible for review of safety of the sentinel patients and approval of enrollment of additional patients into the study. The DSMB will also have general responsibility for oversight of patient safety in this trial. At its discretion, the DSMB may review any available blinded safety data at any time. The DSMB may also request and review unblinded safety data on any patient(s) or group. The DSMB will also have the authority to pause enrollment and/or request safety-related changes to the study protocol. Details of the DSMB membership and planned reviews of safety will be defined in a separate document (DSMB Charter) which will be finalized before the first subject is randomized in the study.

Further details on the DSMB composition and function will be provided in the DSMB Charter. The charter will include information about procedures for unblinding of safety information.

In addition a separate data monitoring committee will evaluate data for a potential Interim Analysis, see Section 8.5.6

7. INVESTIGATIONAL PRODUCT AND OTHER TREATMENTS

7.1 Identity of investigational product(s)

AZD1419 drug substance is an oligodeoxynucleotide (ODN) comprising 22 deoxyribonucleotides linked through a phosphorothioate backbone. AZD1419 is a TLR9 agonist with 3 CpG motifs. AZD1419 drug substance is produced as a freeze-dried solid. The molecule is produced as the sodium salt. AZD1419 drug substance is produced by solid phase synthesis and is not a biological medicinal product.

AZD1419 drug product is intended for inhalation via nebulization and is supplied as 2 mg/mL, 8 mg/mL and 16 mg/mL solution of AZD1419 in phosphate-buffered saline and will be

administered once weekly using the commercially available and CE marked I-neb[®] Adaptive Aerosol Delivery [ADD] System from Philips Respironics.

Investigational product	Dosage form and strength	Manufacturer
AZD1419	Nebuliser solution 2 mg/mL, 8 mg/ml and 16 mg/mL	AstraZeneca
Placebo	Placebo for AZD1419 nebuliser solution	AstraZeneca

The investigational products will be manufacturing in accordance with Good Manufacturing Practice (GMP) supplied by AstraZeneca.

7.2 Dose and treatment regimens

7.2.1 Study Treatments

A total of 70 eligible patients will be randomly assigned 1:1 to receive 13 inhaled once weekly doses of either placebo or AZD1419 during the conduct of the study. Study drug will be administered at the clinic. All eligible patients will be taking ICS and LABA during the screening period, with SABA as rescue therapy during the study.

All patients randomized to AZD1419 will have 4 mg/week of AZD1419 or placebo for 4 doses. After the 4th dose, the 5th dose will be adapted based on tolerability for the final 9 doses. Refer to Section 4.2.2 for details of the dose adaptation procedure.

Instructions for the I-neb will be provided by AstraZeneca.

7.3 Labelling

Label will be prepared in accordance with Good Manufacturing Practice (GMP) and local regulatory guidelines. The label will fulfil GMP Annex 13 and Medical Device Directive requirements for labelling. The label text will be translated into local language.

7.4 Storage

All study drugs and placebo should be kept in a secure place under appropriate storage conditions. The investigational product labels specify the appropriate storage. The IP storage area must be temperature monitored and the site will maintain documentation of the temperature monitoring. Handling instruction will be provided separately by AstraZeneca.

7.5 Compliance

The administration of all study drugs (including investigational products) should be recorded in the appropriate sections of the Case Report Form.

7.6 Accountability

The study drug provided for this study will be used only as directed in the Study Protocol. The study personal will account for all study drugs dispensed to and returned from the patient. The study personal will account for all study products (I-nebs) received at the site, unused study

drug at site and study drug returned by the patients and for appropriate destruction. Destruction should not take place until approved by responsible person at AstraZeneca. Certificates of delivery, destruction should be signed.

The I-nebs used in the study should be returned to AstraZeneca after study closure.

7.7 Concomitant and other treatments

The ICS, LABA and SABA treatment should be prescribed by the Investigator and provided locally.

7.7.1 Other concomitant treatment

Medication other than that described above, which is considered necessary for the patient's safety and wellbeing, may be given at the discretion of the Investigator and recorded in the appropriate sections of the Case Report Form.

7.8 Post Study Access to Study Treatment (Not applicable)

8. STATISTICAL ANALYSES BY ASTRAZENECA OR DELEGATE

Analyses will be performed by AstraZeneca or its representatives.

A comprehensive Statistical Analysis Plan (SAP) will be prepared prior to first patient randomized and any subsequent amendments will be documented, with final amendments completed prior to unblinding of the data.

All personnel involved with the analysis of the study will remain blinded until the database is locked and all protocol violations are identified.

8.1 Statistical considerations

The primary outcome measure is loss of asthma control, as defined in Section 2.1.1. A number of secondary outcomes will also be considered (detailed below).

For the primary analysis of time to loss of asthma control, loss of control is considered to be permanent, given that patients are withdrawn from the study in such an event. Patients who withdraw from treatment and/or the study will have time to event censored at the first missed visit.

The primary hypothesis will be tested one-sided, with $\alpha=0.05$. All other hypothesis tests will be two-sided, with $\alpha=0.05$. Confidence intervals will be two-sided, at the 95% level

There will be no adjustments for multiplicity.

All efficacy analyses will be based on the Full Analysis Set, but with no imputation of missing values. For the summary statistics and analyses of secondary parameters, all data available at each time point will be used.

Safety analyses will include all patients who receive at least one dose of IMP (safety population) and all safety parameters will be described using the Safety population, using summary statistics presented by treatment group

8.2 Sample size estimate

This trial has about 90% power to yield a statistically significant ($\alpha = 0.05$, 2-sided) difference between the pooled active and placebo groups in time to loss of asthma control given that the cumulative number of controlled subjects at week 52 is 20% and 60% for control versus active respectively. Assuming a drop-out of about 10-15%, this will require about 70 patients in total (32 events).

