The investigational product, AZD1419 or matching placebo, will be administered once weekly using the commercially available and CE marked I-neb[®] Adaptive Aerosol Delivery [ADD] System from Philips Respironics.

AZD1419/placebo is supplied as a solution at a concentration of 2 mg/mL, 8 mg/mL and 16 mg/mL in phosphate-buffered saline.

Three inhaled dose levels of AZD1419/placebo, 1 mg, 4 mg and 8 mg may be investigated in a 12 week regimen consisting of 4 once weekly inhaled doses of 4 mg followed by 8 weeks of

inhaled doses of 1 mg, 4 mg, or 8 mg. The maximum possible dose that any patient will receive during the study is 8 mg.

The placebo for this trial is phosphate-buffered saline, pH 7.2.

Statistical methods and sample size

The primary efficacy variable is the time to loss of asthma control, and the primary analysis is to compare the time to loss of asthma control for AZD1419 with placebo. The time to loss of control in the AZD1419 group will be compared to that of the placebo group using a log rank test (with accompanying Kaplan-Meier plot). The hypothesis test will be one-sided, with $\alpha=0.05$.

The secondary outcome variables listed above will be analysed longitudinally using all measurements taken over the course of the study. Continuous variables will be modelled using mixed effects models; categorical outcomes will be modelled using generalized estimating equations. Additionally, all outcomes will be summarized by treatment group at each measurement time point.

This trial has about 90% power to yield a statistically significant ($\alpha = 0.05$, 2-sided) difference between the pooled active and placebo groups in time to loss of asthma control given that the cumulative number of controlled subjects at week 52 is 20% and 60% for control versus active respectively. Assuming a drop-out of about 10-15%, this will require about 70 patients in total (32 events).

TABLE OF CONTENTS

PAGE

TITLE PAGE.....	1
VERSION HISTORY	2
PROTOCOL SYNOPSIS	3
TABLE OF CONTENTS	7
1. INTRODUCTION	15
1.1 Background and rationale for conducting this study	15
1.2 Rationale for study design, doses and control groups.....	16
1.3 Benefit/risk and ethical assessment.....	17
1.4 Study Design	19
2. STUDY OBJECTIVES.....	21
2.1 Primary objective	21
2.1.1 Definition of Loss of asthma control	21
2.2 Secondary objectives	21
2.3 Safety objectives	22
2.4 Exploratory objectives	22

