8.4.2 Calculation or derivation of efficacy variables

8.4.2.1 Time to loss of asthma control

The primary outcome variable, loss of asthma control, is defined in Section 2.1.1.

Time to loss of asthma control will be censored at 52 weeks for patients who do not experience loss of asthma control during the 52-week study period.

For patients who withdraw from the study without reporting loss of asthma control, time will be censored at the date of withdrawal, if known, else at the patient's last clinical visit plus one day.

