1.3 Number of patients

This trial has about 90% power to yield a statistically significant ($\alpha = 0.05$, 2-sided) difference between the pooled active and placebo groups in time to loss of asthma control given that the cumulative number of controlled patients at week 52 is 20% and 60% for control versus active respectively. Assuming a drop-out of about 10-15%, this will require about 70 patients in total (32 events).

Approximately 135 patients have been enrolled to achieve 81 randomised patients.

Figure 1
Study flow
chart

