4. ANALYSIS METHODS

4.1 General principles

The analysis of the study outcome variables will include all data captured during the 52-week double blind treatment and follow-up period. This includes data regardless of whether IP was prematurely discontinued or delayed, and/or irrespective of protocol adherence, unless the patient withdraws consent or assent to study participation.

A summary table which counts patients who have been incorrectly randomised and who received incorrect treatment will be presented.

Summary data will be presented in tabular format by treatment. Categorical data will be summarized by the number and percentage of patients in each category. Continuous variables for parametric data will be summarized by descriptive statistics including N, mean, (standard deviation) SD, median, and range.

Minimum and maximum values will be reported to the same degree of precision as the raw data unless otherwise stated. Mean, median, SD, confidence intervals (CIs), geometric mean and CV will be reported to one further degree of precision. Percentage frequencies will be presented to one decimal place.

Given the number of endpoints in the secondary analyses, multiplicity procedures will not be used to attempt to control 'alpha' across all secondary endpoints.

All data will be listed. Data listings will be sorted by treatment and subject number. Summaries by visit will include baseline but not visits intended for screening and randomisation.

All hypothesis testing will be reported using 2-sided tests except for the primary analysis which will be 1-sided and the p-value will be presented to 4 decimal places. Where confidence

intervals (CI) are presented for treatment comparisons these will be presented as 2-sided 95% CIs.

Plots of data by visit or visit window will cover the entire study period including follow-up.

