4.2.4 Analysis of the primary variable

Under a proportional hazard assumption, we can define the hazard ratio as $\theta = H_A(t)/H_B(t)$ for all $t \leq \tau$, τ is the largest observation time. A represents the active treatment arm (AZD1419), B represents placebo and $H(t)$ is the hazard function. To compare the effect of active treatment AZD1419 to placebo group, a log-rank (Mantel-Cox χ^2) test will be carried out using the SAS[®] procedure PROC LIFETEST, where the null hypotheses will be:

$$H_0: \theta = 1$$

$$H_1: \theta < 1$$

The null hypothesis (H_0) is that during the 52-week double-blind treatment period, the time to loss of asthma control in the AZD1419 arm is equal to the corresponding time to loss of asthma control in the placebo arm. The alternative hypothesis (H_1) is that the time to loss of asthma control in the active arm (AZD1419) is longer than in the placebo arm.

Time to loss of asthma control will be displayed graphically using a Kaplan-Meier plot (time axis, will be time from randomisation).

A Cox proportional hazard model will be fitted to the data to compare the treatments using the SAS[®] procedure PROC PHREG. Results of the analysis will be summarized as hazard ratio, 2-sided 95% confidence interval and p-value comparing AZD1419 with placebo. The hypothesis test will be 1-sided, with $\alpha=0.05$. The covariates for inclusion in the statistical model are described in Section 4.2.1.

For patients who withdraw from the study without reporting loss of asthma control, time will be censored at the date of withdrawal, if known, else at the patient's last clinical visit plus one day.

The assumptions underlying the statistical model will be explored. If the proportional hazards assumption does not hold then alternative methods will be explored which may include the following: 1) Extend the model to include exposure-time interaction term or 2) if the variable for which there is evidence of non-proportional hazards is a confounder, rather than the main exposure of interest then regression may be stratified.

Sensitivity analysis will be performed on the primary variable, see Section 5.1.

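### The sample size sentence gives about 90% power for a two-sided 0.05 test, but the primary log-rank test is one-sided at 0.05; state the power for the test that will be run

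*Protocol*

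**What the plan says.** **Sizing.** The same sentence stands in the Protocol synopsis, Protocol 8.2 and SAP 1.3. It claims about 90% power at alpha 0.05, "2-sided) difference between the pooled active and placebo groups in time to loss of asthma control". It assumes that 20% of placebo and 60% of active patients are still controlled at week 52, and it arrives at 32 events and about 70 patients, allowing for 10-15% drop-out. No formula is named. SAP 1.3 then adds that "Approximately 135 patients have been enrolled to achieve 81 randomised patients".

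**Test.** The synopsis and Protocol 8.5.4 say of the primary log-rank comparison: "The hypothesis test will be one-sided", with alpha 0.05. Protocol 8.1 agrees: "The primary hypothesis will be tested one-sided", again at 0.05. SAP 4.1 sets the primary analysis apart: "All hypothesis testing will be reported using 2-sided tests except for the primary analysis which will be 1-sided". SAP 4.2.4 repeats one-sided 0.05. SAP section 6, the list of departures from the protocol, records no change of sidedness.

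**Interval and follow-up.** Protocol 8.1 sets a general rule: "Confidence intervals will be two-sided, at the 95% level". SAP 4.2.4 applies it to the Cox model: "Results of the analysis will be summarized as hazard ratio, 2-sided 95% confidence interval and p-value comparing AZD1419 with placebo". Follow-up is of fixed length: "Time to loss of asthma control will be censored at 52 weeks for patients" without an event (Protocol 8.4.2.1; the same rule is in SAP 3.2).

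**The concern.** A power statement describes one particular test. Here the test in the sizing sentence and the test in the analysis sections differ in sidedness at the same nominal alpha, and the synopsis contains both within a few lines. One of two things must be wrong: either the 90% does not belong to the planned test, or the label two-sided does not belong in the sentence. A reader cannot tell which, because no formula is given.

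What is at stake is a correct description of the design. Taken alone, the sizing sentence implies a 2.5% chance of a false claim of benefit, whereas the planned test allows 5%. The SAP carries the sentence forward unchanged next to a randomised number of 81, so the stated power matches neither the planned test nor the trial as recruited.

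**Working it through.** **Inputs.** 20% and 60% controlled at week 52, 32 events, about 70 patients, 10-15% drop-out, stated power about 90% (Protocol 8.2). Allocation 1:1 (Protocol 3.5). Censoring at 52 weeks (Protocol 8.4.2.1). 81 randomised (SAP 1.3). Normal quantiles: 1.960 (two-sided 0.05), 1.645 (one-sided 0.05), 1.2816 (90% power).

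**1. Hazard ratio.** Under proportional hazards, HR = ln(0.6)/ln(0.2) = 0.3174, so |ln HR| = 1.1476.

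**2. Reproducing the 32 events.**
- Schoenfeld, d = 4(z_alpha + z_power)² / (ln HR)²: two-sided 31.9; one-sided 26.0.
- Freedman, d = (z_alpha + z_power)² × [(1 + HR)/(1 − HR)]²: two-sided 39.1; one-sided 31.9.

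So 32 events for 90% power comes either from Schoenfeld two-sided or from Freedman one-sided. The patient number does not separate them: 32/0.6 = 53.3, rounded up to 54, which is 60 to 64 after 10-15% drop-out. That is below 70 on either reading.

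**3. Power at 32 events.**

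| Formula | Two-sided 0.05 | One-sided 0.05 (planned) |
|---|---|---|
| Schoenfeld, Phi(√d/2 × 1.1476 − z) | 90.1% | 94.5% |
| Freedman, Phi(√d × (1 − HR)/(1 + HR) − z) | 83.4% | 90.1% |

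For Schoenfeld one-sided: 5.657/2 × 1.1476 = 3.246, and 3.246 − 1.645 = 1.601, giving 94.5%. For Freedman one-sided: 5.657 × 0.5182 = 2.931, and 2.931 − 1.645 = 1.286, giving 90.1%.

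A log-rank simulation with exponential times (54 patients, mean 32.4 events, 8,000 runs) gave 89.9% two-sided and 94.5% one-sided, which supports Schoenfeld.

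**4. The 81 randomised.** Because follow-up is fixed at 52 weeks, the event count follows from the number randomised. Let l be the loss-of-control hazard over 52 weeks (−ln 0.2 for placebo, −ln 0.6 for active) and g = −ln(1 − drop-out). Expected events per arm are (81/2) × l/(l + g) × (1 − exp(−(l + g))). The total is 46.6 at 10% drop-out and 45.6 at 15%, so about 46. This assumes exponential event and drop-out times and that all 81 received study drug and so enter the full analysis set. Allowing no events before the week 6 taper changes little (44.9 to 46.1 in simulation).

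Power of the planned one-sided test at 46 events: Schoenfeld 98.8%; Freedman 96.9%; simulation with 41 and 40 patients per arm (20,000 runs for each drop-out rate) 98.7%.

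**5. Interval and test.** The approximate significance boundary is HR = exp(−2z/√d). At 46 events it is 0.561 for two-sided 0.05 and 0.616 for one-sided 0.05. At 0.616 the approximate 95% interval is 0.35 to 1.10 and the 90% interval is 0.38 to 1.00. With 81 patients, the simulated chance of a result between the boundaries is 1.4-1.8% at HR 0.317 and 2.5% with no effect.

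**The case against.** **Little depends on it.** Sizing for a two-sided test and then testing one-sided at the same alpha errs towards more power. Randomisation is already reported, so no sample size decision remains. This stands, and it limits the point to correcting a wrong description. It does not remove the point, since the sentence still attaches a power figure to a test that is not planned.

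**The figure may be right.** Under Freedman the 90% already belongs to the one-sided test. This stands too: the documents do not show that the 90% is wrong, only that the figure and its label cannot both describe the planned test.

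**A reader might infer a concealed error rate.** The documents do not support that. One-sided 0.05 is stated in the synopsis, Protocol 8.1 and 8.5.4, and SAP 4.2.4, and SAP 4.1 singles out the primary analysis as the exception. A planning sentence does not set the error rate of the test.

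**A reader might infer that the 95% interval is an error,** because a significant result could come with an interval that includes 1. It is a stated convention in both documents, and no section makes the interval a success criterion. Nor would a 90% interval match the test exactly: the log-rank test is unadjusted, while the planned interval comes from a Cox model with age and gender (SAP 4.2.1, 4.2.4).

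**Timing.** SAP section 5 plans an administrative interim analysis, which Protocol 8.5.6 describes as unblinded and done by staff outside study conduct. The edit corrects a description and leaves the test unchanged, but blinded staff should make it.

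**Conclusion.** The point holds as a mislabelled power statement in both documents. For the planned one-sided 0.05 test at HR 0.317 and 32 events, power is about 94.5% by Schoenfeld, with simulation in agreement, or 90.1% by Freedman. In the first case the quoted 90% belongs to a different test and understates the planned test's power by about 4.5 points; in the second only the word two-sided is wrong. Both rest on proportional hazards with the hazard ratio implied by 20% against 60%.

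A reader might go further and conclude that the trial is underpowered or that the success rule is ambiguous as to sidedness. Neither follows. Power for the planned test is at least the stated 90% under both formulas, and higher with 81 randomised. One-sided 0.05 is specified consistently for the primary test.

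**What to change.** Keep the one-sided 0.05 log-rank test. Before unblinding, correct SAP 1.3 in one of two ways, according to the formula used:

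- **Schoenfeld:** *For the planned one-sided log-rank test at alpha = 0.05 and a hazard ratio of 0.317 (20% against 60% controlled at week 52), 32 events give about 94.5% power (Schoenfeld).*
- **Freedman:** keep about 90%, replace two-sided with one-sided, and name the formula.

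Make the same correction in the Protocol synopsis and 8.2 if the protocol is amended.

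If the figure is updated for the 81 randomised, use one labelled method throughout and state the assumptions (52-week censoring, exponential times, 10-15% drop-out): about 46 events, with about 99% power by Schoenfeld or simulation, or about 97% by Freedman. Do not put a Freedman figure beside an unlabelled simulated one.

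Optional, and not corrections of an error: in SAP 4.2.4, add a two-sided 90% interval for the hazard ratio beside the 95% interval, noting that it matches the unadjusted log-rank test only approximately; and state that the one-sided log-rank p-value decides the primary result, with the adjusted Cox model, listed in SAP section 6 as an addition, as supportive.

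**Cost.** A short SAP amendment, which Protocol section 8 allows until unblinding. No extra patients, no loss of power and no change to the decision rule. The protocol need not be amended for this alone; a substantial amendment would need ethics committee approval (Protocol 10.5).
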